Unique study approval ID (Sweden): 2019-05490

Official title: Improving care for children with congenital heart disease by cardiovascular biomarker profiling and advanced non-invasive cardiac imaging techniques.

Statistical analysis plan (date): 25th of Oct. 2020

Study protocol summary:

Study type & outcome measure for cases:

- Case-control study to evaluate diagnostic usefulness of non-invasive cardiac imaging measures and cardiovascular biomarkers in children.
- Need for open heart surgery or cardiac catheter intervention to treat predefined congenital heart disease lesions leading to pulmonary over-circulation (as below).

Enrolment:

After local advertisement and written informed consent (dedicated healthcare regions in Sweden).

Controls (0-17 years) without history or presence of cardiovascular disease at enrolment:

Number of assessments: 1 (at enrolment)

Type of assessments in local paediatric cardiology ambulatory / out-patient clinic settings:

1. Clinical evaluation cardiovascular examination by paediatric cardiologist
2. Standard 12 lead ECG recording
3. Transthoracic echocardiography examination (predefined standard paediatric protocol including but not limited to 2D, Doppler, TDI)
4. Cardiac magnetic resonance (CMR) evaluation of the heart using predefined sequence protocol (including 4D flow assessments) for comparison to cases reaching outcomes (matched subgroup)
5. Peripheral blood sampling for cardiovascular biomarker batch analysis (O-link proximity extension assay of 96 markers and quantitative analysis of selected biomarkers, e.g. NT-pro-BNP)
6. Optional saliva sampling at enrolment and/or retrieval of dried blood samples from neonatal screening laboratory if available for batch analysis and comparison to standard blood sample cardiovascular biomarkers (O-link proximity extension assay of 96 markers and quantitative analysis of selected biomarkers, e.g. NT-pro-BNP)

Cases (0-17 years) without treated congenital heart disease by open heart surgery or cardiac catheter intervention at enrolment:

Included lesions of congenital heart disease leading to pulmonary over-circulation:

- Atrial septal defect (ASD)
- Ventricular septal defect (VSD)
- Patent ductus arteriosus (PDA)
- Partial anomalous pulmonary venous drainage (PAPVD)
- Aorto-pulmonary window (APW)

Number of assessments:

- Minimum 2 (at enrolment and 6-12 months after outcome is reached)

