- Maximum 4 (at enrolment and annually to a max. follow-up of 3 years if not reaching outcome)

Type of assessments in local paediatric cardiology hospital / out-patient clinic settings:

1. Clinical evaluation cardiovascular examination by paediatric cardiologist
2. Standard 12 lead ECG recording
3. Transthoracic echocardiography examination (predefined standard paediatric protocol including but not limited to 2D, Doppler, TDI)
4. Cardiac magnetic resonance (CMR) evaluation of the heart using predefined sequence protocol (including 4D flow assessments) for subjects reaching outcome (undergoing open heart surgery / cardiac catheter intervention) on hospital admission before treatment and 6-12 months after intervention in ambulatory setting.
5. Peripheral blood sampling for later cardiovascular biomarker batch analysis (proximity extension assay and quantitative analysis for selected biomarkers, e.g. NT-pro-BNP)
6. Optional saliva sampling at enrolment and/or retrieval of dried blood samples from neonatal screening laboratory if available as well as optional cardiovascular tissue sampling at time of open heart surgery for batch analysis and comparison to standard blood sample cardiovascular biomarkers (O-link proximity extension assay of 96 markers and quantitative analysis of selected biomarkers, e.g. NT-pro-BNP)

Table summarizing study protocol:

Type of assessment	Subjects	Enrolment	1 year	2 years	3 years
Clinical evaluation	Controls	X	-	-	-
	Cases	X	X	X	X
12-lead ECG	Controls	X	-	-	-
	Cases	X	X	X	X
Transthoracic echocardiography	Controls	X	-	-	-
	Cases	X	X	X	X
Cardiac magnetic resonance *	Controls	X = 1 assessment for controls at enrolment			
	Cases	X = 2 assessments for cases reaching outcome (1 st on admission for intervention & 2 nd 6-12 months post intervention)			
Peripheral blood sampling	Controls	X	-	-	-
	Cases	X	X	X	X

Optional saliva / dried blood sampling	Controls	X	-	-	-
	Cases	X	X	X	X
Optional cardiovascular tissue sampling	Controls	-			
	Cases	X (1 sample for subgroup of cases undergoing open heart surgery)			

*) Subgroup of cases reaching outcome during study and subgroup of matched controls.

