Unique study approval ID (Sweden): 2019-05490

Official title: Improving care for children with congenital heart disease by cardiovascular biomarker profiling and advanced non-invasive cardiac imaging techniques.

Statistical analysis plan (date): 25th of Oct. 2020

Aims:

Diagnostic test evaluations of the cardiovascular system in paediatric controls and cases of defined congenital heart disease lesions, in line with e.g. STARD guidelines, to improve the early prediction of the studied outcome (need for open heart surgery or cardiac catheter intervention in cases).

Diagnostic methods:

1. Echocardiography evaluation:

- selected echocardiographic measure (test individual measures) will be selected to predict outcome (need for open heart surgery or cardiac catheter intervention)

- selected echocardiographic measures (test group of measures) will be selected to predict outcome (as above)

2. Cardiac magnetic resonance (CMR) evaluation:

- selected CMR measure (test individual measures) will be selected to predict outcome (as above)

- selected CMR measures (test group of measures) will be selected to predict outcome (as above)

3. Cardiovascular biomarkers:

- selected cardiovascular biomarker (test individual markers) will be selected to predict outcome (as above)

- selected cardiovascular biomarkers (test groups of markers) will be selected to predict outcome (as above)

Data collection:

- estimation of sample size based on previous studies (power 0.8, alpha 0.05)

- clinical data collection according to predefined criteria (anonymised electronic database)

- electronic storage of echocardiography / cardiac magnetic resonance imaging for analysis

- storage of cardiovascular biomarker samples under standardised conditions until batch analysis

- anonymised data analysis using established statistical methods

Data analysis:

- descriptive statistics / frequency tables of all enrolled subjects (n, %, mean/SD, median/IQR).

- parametric / non-parametric tests to compare controls and cases and changes in cases over follow-up period of study

- logistic regression modelling to identify risk factors / create models that are suitable to predict outcome in cases (need for open heart surgery or cardiac catheter intervention)

- receiver operating characteristics curves (ROC) / area under the curve (AUC) analysis for proposed new diagnostic tests that may help to predict outcome in cases (see above)

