- propose risk factor scoring system to predict outcome in cases (see above)

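### The echo and biomarker models have no validation step: if one set of cases serves for selection, fitting and AUC, as the listed steps imply, the AUC and risk score will be optimistic

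*SAP*

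**What the plan says.** SAP, Diagnostic methods, lists single and grouped measures for each modality. For echocardiography: "selected echocardiographic measures (test group of measures) will be selected to predict outcome (as above". For biomarkers: "selected cardiovascular biomarkers (test groups of markers) will be selected to predict outcome (as above". The outcome is surgical or catheter treatment of the lesion.

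SAP, Data analysis, then gives three further steps, all aimed at prediction in cases: "logistic regression modelling to identify risk factors / create models that are suitable to predict outcome in cases"; "receiver operating characteristics curves (ROC) / area under the curve (AUC) analysis for proposed new diagnostic tests"; and "propose risk factor scoring system to predict outcome in cases (see above".

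On size, SAP, Data collection, says only "estimation of sample size based on previous studies (power 0.8, alpha 0.05". No sample size, event count or effect size follows.

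On the number of candidate markers, the Protocol's list for controls (item 5) gives "O-link proximity extension assay of 96 markers and quantitative analysis of selected biomarkers, e.g. NT-pro-BNP". For the cases' main blood sample (item 5) it gives no number: "Peripheral blood sampling for later cardiovascular biomarker batch analysis (proximity extension assay and quantitative analysis for selected biomarkers, e.g. NT-pro-BNP". That this is the same 96-marker panel is inferred from the next item for cases, which compares 96-marker optional samples with the standard blood sample. The number of echo candidates is not given.

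Neither document mentions a split sample, cross-validation, bootstrap, shrinkage, calibration, a second cohort, or a marker set fixed in advance.

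**The concern.** The AUC and the score are the SAP's route to its stated aim of early prediction. The listed steps run from choosing measures for their ability to predict the outcome, through fitting, to measuring performance, with one set of cases and nothing in between. An AUC computed in the children who supplied the selection and the coefficients describes those children and overstates performance in new ones. There are two sources: choosing the measures that happened to separate best, and fitting coefficients to the same outcomes. A score built from those coefficients would also tend to give predicted risks that are too extreme. A reader of the report could not tell how much of the AUC is real.

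**Working it through.** **No figure to reproduce.** The documents state no AUC, sample size or event count, so the check is an illustration under assumed inputs, for biomarkers only.

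**Inputs.** From the documents: 96 markers (inferred for cases, as above) and a logistic model. Assumed: numbers of events/non-events; marker correlation 0, 0.3 or 0.5; the five markers with the largest |AUC - 0.5| enter the model; either no real marker, or three with a standardised mean difference (SMD) of 0.5, 0.8 or 1.2. There were 300 simulated datasets per setting, each model also being tested in 2000 new children.

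**Formulas.** AUC = (R1 - n1(n1 + 1)/2) / (n1 × n0), where R1 is the rank sum of the events. Optimism = apparent AUC - AUC in new children.

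**Noise only (true AUC 0.50; AUC in new children 0.498-0.500).** Ranges are over the three correlations.

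| Events/non-events | Best 5 of 96, apparent | Five fixed markers, apparent |
|---|---|---|
| 30/70 | 0.71-0.79 | 0.63 |
| 50/50 | 0.69-0.77 | 0.62 |
| 100/100 | 0.64-0.70 | 0.58-0.59 |
| 150/350 | 0.60-0.64 | 0.56 |

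Share of the excess due to fitting alone, at 30/70: with correlation 0, (0.633 - 0.50)/(0.791 - 0.50) = 0.46; with correlation 0.5, (0.633 - 0.50)/(0.708 - 0.50) = 0.64. Over all settings the share is 0.43-0.65. The rest is selection.

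**Three real markers, optimism.**

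| Events/non-events | SMD 0.5 | SMD 0.8 | SMD 1.2 |
|---|---|---|---|
| 30/70 | 0.140-0.217 | 0.075-0.109 | 0.034-0.049 |
| 50/50 | 0.119-0.185 | 0.066-0.087 | 0.029-0.039 |
| 100/100 | 0.064-0.089 | 0.031-0.042 | 0.014-0.020 |
| 150/350 | 0.027-0.040 | 0.013-0.021 | 0.006-0.010 |

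**Independent check.** Separate code (400 datasets per setting, uncorrelated markers) gave noise-only apparent AUCs of 0.793 for 100 cases with 30% events, 0.770 for 100 with 50%, and 0.697 for 200 with 50%. The matching values above, at correlation 0, are 0.791, 0.767 and 0.697. The same run covered single markers: the best one of 96 noise markers showed 0.72-0.74 at 50 cases and 0.58-0.59 at 400, against 0.50 in new children.

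**Does the correction need to repeat selection?** Noise at 50/50, correlations 0/0.3/0.5: cross-validation applied only after selection gave 0.721/0.667/0.620. Nested 5-fold cross-validation with 10 repeats gave 0.503/0.503/0.502. It does.

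**Calibration.** For the unpenalised five-marker model at SMD 0.5, the median calibration slope in new children was 0.26-0.50 at 30/70 and 50/50, and 0.81-0.90 at 150/350 (ideal: 1). This is the same problem seen in the score.

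**The case against.** The strongest reply is that the SAP never says selection is made from the data. The Protocol uses the same word for a named group of quantitative assays ("O-link proximity extension assay of 96 markers and quantitative analysis of selected biomarkers, e.g. NT-pro-BNP"), and the echo examination follows a predefined paediatric protocol, so the measures might be chosen beforehand. This stands as a limit. On that reading only the fixed-marker column applies to a multi-marker model. For a single measure with its direction fixed in advance, neither source of optimism arises, because AUC depends only on ranks. It does not remove the point, since the SAP names no such measures and still plans grouped models.

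A second reply is that the SAP cites STARD and standard methods, and words its tests and score as proposals. Neither citation commits the analyst to a validation step. The tentative wording does mean that the SAP does not claim a validated tool.

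A reader might infer several stronger things that the documents do not support:

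- *That the plan states that the same children are used throughout.* It does not. This follows from one described set of cases and no split.
- *That the tabulated sizes are this study's.* Without a sample size or event count they cannot be.
- *That echo models carry the same excess.* With no number of echo candidates, no size can be given.
- *That a confidence interval almost never reveals the problem.* On noise, a DeLong 95% interval excluded 0.50 in 98-100% of datasets with selection from 96, but in 54-62% with five fixed markers. Both figures are for pure noise, and the SAP names no interval method.
- *That repeated visits inflate the AUC.* Nothing says visits are pooled in the models. In the two-visit schedule the second visit follows the intervention and cannot be a predictor.
- *That the point extends to CMR or to multiple testing across the panel.* Cases not reaching the outcome have no scheduled CMR, so validation would not repair a CMR model within cases. Multiple testing is a separate issue.

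**Conclusion.** The omission is clear from the text. Its effect is conditional. If selection is data-driven and the same children are reused, the AUC and score are optimistic from both sources; if the measures are fixed beforehand, a multi-marker model is still optimistic, from fitting alone. The direction is certain under those conditions, but the size in this study cannot be determined. For the assumed biomarker setting with real signal, the excess runs from about 0.2 (weak signal, few events) to at most 0.01 (strong signal, many events). It is therefore material in a small study or with weak markers, and minor in a large study with strong ones. Nothing in the SAP shows which applies. It is worth correcting before the data are analysed.

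**What to change.** In SAP, Data analysis, for the echo and biomarker models in cases:

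1. State the selection rule, or list the measures if they are fixed in advance.
2. Report AUC with a confidence interval, and calibration, corrected for optimism by resampling that repeats the whole selection and fitting process each time. Bootstrap optimism correction or repeated nested cross-validation would both serve.
3. Label any AUC from the full data as apparent.
4. If more than one pre-outcome visit per child is modelled, resample by child.
5. Label the risk score as needing external validation. Penalised coefficients are an option, not a requirement.

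**Cost.** SAP wording and some computing time; no new data or visits. Reported AUCs will be lower and less precise: on noise, the SD of the nested estimate with 10 repeats was 0.065-0.069 at 50/50 and 0.034 at 150/350. Nested cross-validation can also be pessimistic, by up to about 0.03 in small samples (0.030, SE 0.007, at 30/70 with SMD 0.5). That is well below the optimism removed when the signal is weak and events are few, but comparable with it when the signal is strong.

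### The SAP does not say how age is handled when controls and cases aged 0–17 years are compared at enrolment, so an age difference could be read as, or could hide, a disease difference

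*SAP*

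**What the plan says.** The SAP's Data analysis section gives one line to both comparisons: "parametric / non-parametric tests to compare controls and cases and changes in cases over follow-up period of study". It names no covariate, stratum, matched analysis or age-standardised value. The only regression named is "logistic regression modelling to identify risk factors / create models that are suitable to predict outcome in cases". The ROC and scoring lines are likewise about outcome in cases, so none of them covers the comparison with controls.

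The protocol gives both groups the same wide age range:

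- "Controls (0-17 years) without history or presence of cardiovascular disease at enrolment"
- "Cases (0-17 years) without treated congenital heart disease by open heart surgery or cardiac catheter intervention at enrolment"

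Enrolment follows local advertisement, and no age balancing is stated. Matching appears twice, both times with CMR: in item 4 of the controls' assessments and in the footnote to the CMR row of the summary table, "Subgroup of cases reaching outcome during study and subgroup of matched controls". No matching factors are given, and the SAP does not mention matching.

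For follow-up, the protocol has a visit 6–12 months after intervention for cases that reach the outcome, and annual visits for up to 3 years for those that do not. CMR in cases has its own timing: "on hospital admission before treatment and 6-12 months after intervention in ambulatory setting".

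**The concern.** Measures of the heart and circulation can change with age and growth over 0–17 years. A plain two-group test compares the groups as recruited. If controls who answer an advertisement are older or younger on average than the cases, the test picks up age as well as disease. The error can go either way: a measure may look diagnostic because of age, or a real difference may be hidden. Treatment status is not part of this problem, because cases are untreated at enrolment.

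ECG, echocardiography and blood biomarkers are the exposed measures. CMR is partly protected if its matching includes age, but the documents do not say that it does.

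A smaller gap concerns change in cases on the non-CMR measures. The SAP line does not say whether change in untreated children and change after an intervention are reported separately, which visit is the baseline, or how unequal intervals are treated.

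**Working it through.** **Inputs from the documents.** Age 0–17 years in both groups; alpha 0.05 and power 0.8 (SAP, Data collection). There is no sample size, age distribution, age slope or SD, so there is no stated figure to reproduce and the bias cannot be sized. What follows is an illustration.

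**Assumptions.** 50 children per group, age SD 5 years before any truncation, slope 0.1 outcome units per year, no true group effect, two-sided 5% t-test. There are two versions of the scatter:

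- residual variance 0.75, so within-group SD = √(0.75 + 0.1² × 25) = 1.00;
- residual SD 1, so within-group SD = √(1 + 0.1² × 25) = 1.12.

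**Formula.** Spurious standardised difference d = 0.1 × age gap / within-group SD. Rejection rate ≈ P(|Z + d/√(2/50)| > 1.96), where √(2/50) = 0.2.

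**Gap 0.** d = 0, so rejection is 5%.

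**Gap 2 years.**
- SD 1.00: d = 0.20, shift 0.20/0.2 = 1.00, rejection about 17%.
- SD 1.12: d = 0.179, shift 0.89, rejection about 14%.

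**Nominal gap 4 years.** With normal ages the rates are about 50% and 42%, but these ages do not fit the trial. Centred on 8.5 years, the group means are 6.5 and 10.5, and about 11% of children fall outside 0–17. Truncating to 0–17 moves the means to about 7.2 and 9.8, an actual gap of about 2.6 years, and reduces the age SD to about 3.95. Then:
- residual variance 0.75: SD = √(0.75 + 0.01 × 15.6) = 0.95, d = 0.256/0.95 = 0.27, shift 1.35, rejection about 27%;
- residual SD 1: SD = √(1 + 0.01 × 15.6) = 1.08, d = 0.256/1.08 = 0.24, shift 1.19, rejection about 22%.

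The usable range is therefore roughly 14–27% for an actual gap of 2 to 2.6 years. Simulation agrees. Regression on group and age rejects about 5% throughout. That is expected, because the data were generated and fitted with a straight line in age; it does not test a flexible model.

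**Cost of adjustment.** Ratio of the adjusted to the unadjusted standard error = √((1 − R²)(1 + g²/4)), where g is the age gap in SDs and R² the within-group share of variance explained by age. For g = 0.8:
- R² = 0: √1.16 = 1.077, a rise of 8%;
- R² = 0.1: √(0.9 × 1.16) = 1.022, a rise of 2%;
- R² = 0.3: √(0.7 × 1.16) = 0.901, a fall of 10%.

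**Change in cases, non-CMR measures.** Untreated visits fall 12, 24 and 36 months after enrolment. A post-intervention visit falls between 0 + 6 = 6 and 36 + 12 = 48 months after enrolment, or no later than 36 if the 3-year limit covers every visit. The one SAP line covers both kinds of visit without a rule. The schedule does let each visit be classified, so the data are there and only the analysis rule is absent.

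**The case against.** **The main aim is prediction within cases.** This stands. The SAP's diagnostic methods, logistic regression, ROC and scoring all serve prediction of intervention, and an age imbalance between controls and cases does not affect them. The SAP never calls the case-control contrast primary. It is nevertheless a planned analysis in what the protocol calls a case-control study, and the only stated use of the control data beyond description.

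**Silence is not a plan to ignore age.** This also stands in part. The SAP's wording is a class label that could include paired or adjusted tests, and the predefined echocardiography protocol, which is not among the documents, may cover indexing to body size. The supportable claim is that age handling is not stated.

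**The footnote could mean that all controls are matched.** Tying matching to CMR alone is the likelier reading, but the sponsor should be asked.

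**Stronger readings that the documents do not support.**
- A reader might infer that the case-control results will be biased. That needs an actual age imbalance and a measure that varies with age, and the documents give data on neither.
- A reader might infer that untreated and post-intervention changes will be pooled. No text plans that.
- A reader might infer that, with CMR before and 6–12 months after intervention, growth and intervention effects are inseparable. The short interval makes them hard to estimate apart from the paired scans alone, which is a matter of precision. Size-indexed values or the control scans could help, under assumptions.

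**Conclusion.** The point holds for the enrolment contrasts of ECG, echocardiography and blood biomarkers: the SAP names tests without age handling for two groups that each span 0–17 years, and no other line fills the gap. This is a credible risk, not a demonstrated bias. Under the assumptions shown, an actual mean age gap of 2 to 2.6 years raises false rejections from 5% to roughly 14–27%. With no gap, or a measure that does not vary with age, the level stays at 5%. For CMR the open question is which factors are matched and whether they enter the analysis. For change in cases, the point is limited to a missing reporting rule. The SAP should be changed, but the prediction work that serves the main aim does not depend on it.

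**What to change.** 1. Analyse each case-control contrast at enrolment by regression of the measure (log-transformed where skewed) on group, adjusted for age in flexible form, and for sex if recorded. Use size-indexed or age-standardised values for dimensions that scale with growth.
2. For CMR, state the matching factors and carry them into the analysis together with age at scan, because case scans are taken on admission and not at enrolment. Clarify whether any matching extends to controls outside the CMR subgroup.
3. For change in cases on ECG, echocardiography and biomarkers, report untreated change and post-intervention change separately as within-child differences. Name the baseline visit (for example the last untreated visit), give the interval, and note that post-intervention change also includes growth.

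**Cost.** SAP wording, a little more analysis work and a few degrees of freedom. At an age gap of 0.8 SD the standard error rises by at most about 8%, when age explains none of the variance, and it falls when age explains a good share. Sex and body size are not listed among the assessments, so confirm that both are recorded. No extra visit is needed.

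### Does the analysis of change in cases need its time points fixed, given that follow-up crosses the intervention and the summary table does not fully match the text?

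*SAP*

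**What the plan says.** The SAP's Data analysis section has one line on change. Alongside the comparison of controls with cases, it plans parametric or non-parametric tests of "changes in cases over follow-up period of study". It names no visits and no pairing.

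The protocol describes cases as "without treated congenital heart disease by open heart surgery or cardiac catheter intervention at enrolment". Under Number of assessments it gives two follow-up paths:

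- for a case who reaches the outcome: "Minimum 2 (at enrolment and 6-12 months after outcome is reached";
- for a case who does not: "Maximum 4 (at enrolment and annually to a max. follow-up of 3 years if not reaching outcome".

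The list of assessment types for cases follows directly. Clinical evaluation, ECG and echocardiography carry no timing of their own. Neither does blood, which is listed as "Peripheral blood sampling for later cardiovascular biomarker batch analysis". CMR has its own timing, "on hospital admission before treatment and 6-12 months after intervention in ambulatory setting". The last item reads "Optional saliva sampling at enrolment and/or retrieval of dried blood samples from neonatal screening laboratory if available as well as optional cardiovascular tissue" sampling at surgery.

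The Table summarizing study protocol has columns for enrolment and 1, 2 and 3 years. For cases, the rows for clinical evaluation, ECG, echocardiography, blood and optional saliva / dried blood are marked in all four columns. Only the CMR row mentions an assessment 6-12 months after intervention.

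**The concern.** The study outcome is the intervention itself. In a child who is treated, a difference between an early and a late value includes the effect of closing the shunt. In a child who is not treated, it reflects the lesion's natural course and growth. A single analysis of change that mixed the two would have no clear meaning, and the SAP line does not rule that out.

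The table appears to make this worse. Read alone, it has cases attending annually whether treated or not, with no post-outcome echocardiogram, ECG or blood sample. Enrolment takes place in "dedicated healthcare regions in Sweden". Clinics that scheduled from the table and clinics that scheduled from the text could collect post-intervention data at different times, and a missed visit cannot be recovered at analysis. CMR has a stated before/after pair; the other modalities have no stated measurement at admission. Their before/after change might therefore span a longer period of growth.

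**Working it through.** The SAP states no sample size, event count or effect size, so there is no figure to reproduce. The check compares text with table and then works out the intervals.

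**1. Visit counts.** A case not reaching outcome has enrolment plus three annual visits: 1 + 3 = 4, the stated maximum. A case treated during the third year, with annual visits stopping at outcome, has enrolment, year 1, year 2 and the post-outcome visit: 3 + 1 = 4. The text's two paths are coherent.

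**2. Post-outcome visit, text against table.** The text sets the visit immediately before listing the assessments. Four items (clinical evaluation, ECG, echocardiography, blood) have no other timing, so the natural reading is that they are done at that visit. The table omits it from those four rows and includes it in one (CMR). If treatment occurs at month t, with t between 0 and 36, the visit falls between t + 6 and t + 12, so it can be as late as 36 + 12 = 48 months. An event-driven visit of this kind does not fit columns fixed at 12, 24 and 36 months. The table is an incomplete summary.

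**3. Annual visits.** The text makes them conditional on not having reached the outcome; the table shows no condition. Read as a maximum schedule, the table agrees with the text. Calculations of how often an annual visit falls inside the 6-12 month window would apply annual visits to children already treated. The text does not schedule those visits, so such figures do not describe this plan.

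**4. Saliva / dried blood in cases.** The text gives one time for saliva (enrolment); the table marks four. The row also covers retrieved neonatal dried blood, for which the text gives no time, but annual marks fit a retrieved neonatal sample poorly. For controls, text and table agree.

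**5. Before/after interval by modality.** This assumes treatment soon after admission.

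| Pre-intervention value | Interval to post-outcome value |
|---|---|
| CMR at admission | 6 to 12 months, midpoint 9 |
| Last scheduled visit, 0-12 months before treatment | 0 + 6 = 6 to 12 + 12 = 24 months; mean 6 + 9 = 15 |
| Enrolment, 0-36 months before treatment | 0 + 6 = 6 to 36 + 12 = 48 months |
| Echocardiography, ECG or blood at admission, if taken | 6 to 12 months, as for CMR |

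The mean of 15 assumes that treatment is spread evenly within each year and the post-outcome visit evenly over its window. With treatment skewed early or late within years (Beta(1,2) or Beta(2,1)), the mean is 13 or 17 months. The documents give no distribution of treatment times, and they neither require nor exclude echocardiography, ECG or blood at admission.

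**6. What depends on it.** The SAP's logistic regression, ROC analysis and risk score aim to predict the intervention. A value taken afterwards cannot serve as a predictor of it, so these analyses do not depend on how change is defined. The SAP's biomarker section does not mention saliva.

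**The case for a change.** The strongest argument for a change is that it is cheap and guards against an irreversible loss. Two sentences in the SAP could separate change before intervention from paired change across it and name the visits. A footnote could put the post-outcome visit into the four rows. A clinic that did work from the table alone could miss the window, and no analysis would restore the data.

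Part of this stands. The SAP names no contrast, four table rows are incomplete, and the saliva row disagrees with the text.

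The rest is weaker. The loss requires clinics to follow a summary table against the protocol text, and nothing in the documents suggests that they would. The longer interval for echocardiography, ECG and blood disappears if they are measured at admission. Naming the contrasts now would also mean choosing between enrolment and the last pre-intervention value as baseline, and both are defensible. Enrolment is the only pre-intervention value that the text guarantees for these modalities. Separate contrasts have costs too: fewer children in each, nothing contributed to pre-intervention change by a child treated before the first annual visit, and a pre-intervention series that ends selectively when a child is treated.

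**Conclusion.** No change to the plan is called for. The missing contrast is a gap in a secondary, descriptive analysis that a competent analyst fills by keeping values from before and after treatment apart; no rule in the SAP directs otherwise. The protocol text fixes the post-outcome visit and the condition on annual visits, so the table's omission in four of the five core rows is incompleteness in a summary. The saliva entry, one time point against four, is a clerical slip in an optional sample.

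The only quantity that can be derived is the possible difference in before/after interval: 6-12 months for CMR against 6-24 months for the other modalities (means of 9 and 15 with even timing). It holds only if nothing but CMR is measured at admission and the last scheduled visit is the baseline. Any resulting distortion cannot be sized from the documents. The conclusion rests on clinics following the text and on the visits used being reported with the results.
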